10.1.8 Source Documents

1. Source data must be available at the study site to document the existence of the participants and to substantiate the integrity of study data collected. Source data must include the original documents relating to the study, as well as the medical treatment and medical history of the participant.
2. The investigator must maintain accurate documentation (source data) that supports the information entered in the CRF.
3. The investigator is responsible for ensuring the source data are attributable, legible, contemporaneous, original, accurate and complete whether the data are handwritten on paper or entered electronically. If source data are created (first entered), modified, maintained, archived, retrieved or transmitted electronically via computerized systems (and/or other kind of electronic devices) as part of regulated study activities, such systems must be compliant with all applicable laws and regulations governing use of electronic records and/or electronic signatures. Such systems may include, but are not limited to, electronic medical/health records, protocol-related assessments, AE tracking, electronic clinical outcome assessment and/or drug accountability.
4. Paper records from electronic systems used in place of electronic format must be certified copies. A certified copy must be an exact copy and must have all the same attributes and information as the original. Certified copies must include signature and date of the individual completing the certification. Certified copies must be a complete and chronological set of study records (including notes, attachments, and audit trail information, if applicable). All printed records must be kept in the participant file and be available for archiving.
5. Study monitors will perform ongoing source data review to confirm that the safety and rights of participants are being protected; and that the study is being conducted in accordance with the currently approved protocol and any other study agreements, ICH GCP, and all applicable regulatory requirements.

10.1.9 Study and Site Start and Closure

The sponsor or designee reserves the right to close the study site or terminate the study at any time for any reason at the sole discretion of the sponsor. Study sites will be closed upon study completion. A study site is considered closed when all required documents and study supplies have been collected and a study-site closure visit has been performed.

The investigator may initiate study-site closure at any time, provided there is reasonable cause and sufficient notice is given in advance of the intended termination.

Reasons for the early closure of a study site by the sponsor or investigator may include but are not limited to:

For study termination:

- Discontinuation of further investigational study intervention development

For site termination:

- Failure of the investigator to comply with the protocol, the requirements of the IRB/IEC or local health authorities, the sponsor's procedures or GCP guidelines
- Inadequate or no recruitment (evaluated after a reasonable amount of time) of participants by the investigator
- Total number of participants included earlier than expected

If the study is prematurely terminated or suspended, the sponsor or designee shall promptly inform the investigators, the IRBs/ IECs, the regulatory authorities, and any CRO(s) used in the study of the reason for termination or suspension, as specified by the applicable regulatory requirements. The investigator shall promptly inform the participant and should assure appropriate participant therapy and/or follow-up.

10.1.10 Arrangement for Use of Information and Publication of the Study

Information concerning the test product, patent applications, processes, unpublished scientific data, the IB and other pertinent information is confidential and remains the property of the sponsor. Details should be disclosed only to the persons involved in the approval or conduct of the study. The investigator may use this information for the purpose of the study only. It is understood by the investigator that the sponsor will use the information obtained during the study in connection with the development of the product and therefore may disclose it as required to other clinical investigators or to regulatory agencies. In order to allow for the use of the information derived from this study, the investigator understands that he/she has an obligation to provide the sponsor with all data obtained during the study.

Publication of the study results is discussed in the study agreement.

10.1.11 Quality Assurance

The sponsor is implementing and maintaining quality assurance (QA) and quality control (QC) systems with written SOPs to ensure that studies are conducted and data are generated, documented, recorded, and reported in compliance with the protocol, GCP and applicable regulatory requirement(s). Where applicable, the QA and QC systems and written SOPs of the CRO will be applied.

The sponsor or sponsor's designee may arrange to audit the study at any or all study sites and facilities. The audit may include on-site review of regulatory documents, CRFs and source documents. Direct access to these documents will be required by the auditors.

To support quality around participant safety and reliability of study results, quality tolerance limits (QTLs) are defined and monitored. QTLs represent the acceptable variation of study data, taking into consideration the current state of medical and statistical knowledge about the variables to be analyzed, as well as the statistical design of the study. It is a level, point, or value associated with a parameter that should trigger an evaluation if a deviation is detected to determine if there is a possible systematic issue (i.e., a trend has occurred). The QTLs defined for this study are provided below.

Table 6 Quality Tolerance Limits

QTL #: Name and Parameter	Definition	Parameter Justification
QTL1: Sufficient data for assessment to decide optimal dose of ASP5354 for LN visualization: % missing at least 1 of all below data of anatomical visualization of LN(s) after dosing ASP5354. 
• LN tissue visualized (Y/N)• Visualized tissue is lymphatic in origin based on pathologic confirmation	Number of participants who missed at least 1 of all below data of anatomical visualization of LN(s) after dosing ASP5354 per total number of enrolled participants (%). 
• LN tissue visualized (Y/N)• Visualized tissue is lymphatic in origin based on pathologic confirmation	Since all of the data of anatomical visualization of the LN(s) after dosing ASP5354 is the primary endpoint to determine the optimal dose of ASP5354, missing data points would hinder evaluation of efficacy.
QTL2: Reliable data for assessment of LN visualization by ASP5354: % receiving excluded concomitant medications, listed in [Section 10.5 Appendix 5 List of Excluded Concomitant Medications] in protocol deviated manner	Number of participants who received excluded concomitant medications, listed in [Section 10.5 Appendix 5 List of Excluded Concomitant Medications] in protocol deviated manner per total number of enrolled participants (%).	Since excluded concomitant medication might affect visualization of the LN(s) by ASP5354.

QTL: quality tolerance limit, LN: lymph node

QTL Management Activities:

- For control of risks associated with QTL1: Sufficient data for assessment of anatomical visualization of the LN, refer to [Section 7.1 Efficacy Assessments].
- For control of risks associated with QTL2: Reliable data for assessment of LN visualization by ASP5354, refer to [Section 10.5 Appendix 5 List of Excluded Concomitant Medications].

10.2 Appendix 2 Contraception Requirements

WOCBP, who are eligible for participation in the study, including those who choose complete abstinence, must have pregnancy tests as specified in the Schedule of Assessments [Table 1]. Pregnancy test results must confirm that the participant is not pregnant.

WOMEN OF CHILDBEARING POTENTIAL DEFINITIONS AND METHODS OF CONTRACEPTION DEFINITIONS

A female is considered fertile (i.e., WOCBP) following menarche and until becoming postmenopausal unless permanently sterile.

Females in the following categories are not considered WOCBP

- Premenarchal
- Premenopausal with one of the following (i.e., permanently sterile):
 - Documented hysterectomy
 - Documented bilateral salpingectomy
 - Documented bilateral oophorectomy
- Postmenopausal

A postmenopausal state is defined as at least 12 months after last menstrual bleeding without an alternative medical cause.

In case the last menstrual bleeding cannot be clearly determined, confirmation with more than 1 follicle-stimulating hormone (FSH) measurement of at least > 40 IU/L (or higher per local institutional guidelines) is required.

Females on hormone replacement therapy (HRT) and whose menopausal status is in doubt will be required to use one of the nonestrogen hormonal highly effective contraception methods if they wish to continue their HRT during the study. Otherwise, they must discontinue HRT to allow confirmation of postmenopausal status by repeated FSH measurements before study enrollment.

Documentation of any of these categories can come from the study site personnel's review of the female participant's medical records, medical examination or medical history interview.

CONTRACEPTION GUIDANCE FOR FEMALE PARTICIPANTS OF CHILDBEARING POTENTIAL

Female participants of childbearing potential are eligible for participation in the study if they agree to use one of the highly effective methods of contraception listed below from the time of signing the ICF and until the end of relevant systemic exposure, defined as at least 30 days after final study treatment administration.^a

Highly effective methods of contraception (failure rate of $< 1\%$ per year when used consistently and correctly)^b:

- Combined (estrogen- and progestogen-containing) hormonal contraception associated with inhibition of ovulation
 - Oral

- Intravaginal
- Transdermal
- Progestogen-only hormonal contraception associated with inhibition of ovulation
 - Oral
 - Injectable
 - Implantable
- Other combined (estrogen- and progesterone-containing) methods
 - Vaginal ring
 - Injectable
 - Implantable
 - Intrauterine hormone-releasing system or intrauterine device
 - Bilateral tubal occlusion
- Vasectomized partner

A vasectomized partner is a highly effective contraception method provided that the partner is the sole male sexual partner of the WOCBP and the absence of sperm has been confirmed. If not, an additional highly effective method of contraception should be used.
- Sexual abstinence

Sexual abstinence is considered a highly effective method only if defined as refraining from heterosexual intercourse during the entire period of risk associated with the test product. The reliability of sexual abstinence needs to be evaluated in relation to the duration of the study and the preferred and usual lifestyle of the participant. It is not necessary to use any other method of contraception when complete abstinence is elected.

^a Local laws and regulations may require use of alternative and/or additional contraception methods.

^b Typical use failure rates may differ from those when used consistently and correctly. Use should be consistent with local regulations regarding the use of contraceptive methods for participants participating in clinical studies.

CONTRACEPTION GUIDANCE FOR MALE PARTICIPANTS WITH PARTNER(S) OF CHILDBEARING POTENTIAL

Male participants with female partners of childbearing potential are eligible for participation in the study if they agree to the following during treatment and until the end of relevant systemic exposure defined as at least 30 days after final study treatment administration.^a

- Inform any and all partner(s) of their participation in a clinical drug study and the need to comply with contraception instructions as directed by the investigator
- Use a condom
- Female partners of male participants who have not undergone a vasectomy with the absence of sperm confirmed or a bilateral orchiectomy should consider use of effective methods of contraception

^a Local laws and regulations may require use of alternative and/or additional contraception methods.

10.3 Appendix 3 Adverse Events/Adverse Device Effects: Definitions and Procedures for Recording, Evaluating, Follow-up and Reporting

10.3.1 Definition of Adverse Events

AE Definition:

An AE is any untoward medical occurrence in a patient or clinical study participant, temporally associated with the use of study IP, whether or not considered related to the study IP.

NOTE: An AE can therefore be any unfavorable and unintended sign (including an abnormal laboratory finding), symptom, or disease (new or exacerbated) temporally associated with the use of study IP. This includes events related to the comparator and events related to the (study) procedures.

Events Meeting the AE Definition

- Any abnormal laboratory test results (hematology, clinical chemistry, or urinalysis) or other safety assessments (e.g., ECG, radiological scans, vital signs measurements), including those that worsen from baseline, considered clinically significant in the medical and scientific judgment of the investigator (i.e., not related to progression of underlying disease).
- Exacerbation of a chronic or intermittent pre-existing condition including either an increase in frequency and/or intensity of the condition.
- New conditions detected or diagnosed after study IP administration even though it may have been present before the start of the study.

Events NOT Meeting the AE Definition

- Any clinically significant abnormal laboratory findings or other abnormal safety assessments which are associated with the underlying disease, unless judged by the investigator to be more severe than expected for the participant's condition.
- The disease/disorder being studied or expected progression, signs, or symptoms of the disease/disorder being studied, unless more severe than expected for the participant's condition.
- Medical or surgical procedure (e.g., endoscopy, appendectomy): the condition that leads to the procedure is the AE.
- Situations in which an untoward medical occurrence did not occur (social and/or convenience admission to a hospital).
- Anticipated day-to-day fluctuations of pre-existing disease(s) or condition(s) present or detected at the start of the study that do not worsen.

10.3.1.1 Abnormal Laboratory Findings

Any abnormal laboratory test result (e.g., hematology, biochemistry or urinalysis) or other safety assessment (e.g., vital signs, physical examination or ECGs), including those that worsen from baseline, that is considered to be clinically significant in the medical and

scientific judgment of the investigator and not related to underlying disease, is to be reported as an (S)AE.

Any clinically significant abnormal laboratory finding or other abnormal safety assessment, which is associated with the underlying disease, does not require reporting as an (S)AE, unless judged by the investigator to be more severe than expected for the participant's condition.

Repeating an abnormal laboratory test or other safety assessment, in the absence of any of the above criteria, does not constitute an AE. Any abnormal test result that is determined to be an error does not require reporting as an AE.

10.3.1.2 Potential Cases of Drug-induced Liver Injury

Refer to [Section 10.4 Appendix 4 Liver Safety Monitoring and Assessment] for detailed instructions on drug induced liver injury (DILI). Abnormal values in AST and/or ALT concurrent or with abnormal elevations in total bilirubin (TBL) that meet the criteria outlined in [Section 10.4 Appendix 4 Liver Safety Monitoring and Assessment] in the absence of other causes of liver injury, are considered potential cases of DILI (potential Hy's Law cases; [Temple, 2006]) and are always to be considered important medical events and reported per [Section 10.3.7 Reporting Procedures for Serious Adverse Events/Adverse Device Effects].

10.3.2 Definition of Serious Adverse Events

An SAE is defined as any untoward medical occurrence that, at any dose:

- Results in death
- Is life-threatening

The term "life-threatening" in the definition of "serious" refers to an event in which the participant was at risk of death at the time of the event. It does not refer to an event, which hypothetically might have caused death, if it were more severe.

- Requires inpatient hospitalization or prolongation of existing hospitalization
 - In general, hospitalization signifies that the participant has been detained (usually involving at least an overnight stay) at the hospital or emergency ward for observation and/or treatment that would not have been appropriate in the physician's office or outpatient setting. Complications that occur during hospitalization are AEs. If a complication prolongs hospitalization or fulfills any other serious criteria, the event is serious. When in doubt as to whether "hospitalization" occurred or was necessary, the AE should be considered serious.
 - Hospitalization for elective treatment of a pre-existing condition that did not worsen from baseline is not considered an AE.
- Results in persistent or significant disability/incapacity
 - The term disability means a substantial disruption of a person's ability to conduct normal life functions.
 - This definition is not intended to include experiences of relatively minor medical significance such as uncomplicated headache, nausea, vomiting, diarrhea, influenza,

and accidental trauma (e.g., sprained ankle), which may interfere with or prevent everyday life functions but do not constitute a substantial disruption.

- Is a congenital anomaly/birth defect
- Other situations:
 - Medical or scientific judgment should be exercised in deciding whether SAE reporting is appropriate in other situations such as important medical events that may not be immediately life-threatening or result in death or hospitalization but may jeopardize the participant or may require medical or surgical intervention to prevent one of the other outcomes listed in the above definition. These events should usually be considered serious.
 - Examples of such events include invasive or malignant cancers, intensive treatment in an emergency room or at home for allergic bronchospasm, blood dyscrasias or convulsions that do not result in hospitalization, or development of drug dependency or drug abuse.

If an event is not an AE per definition in [Section 10.3.1 Definition of Adverse Events], then it cannot be an SAE even if serious conditions are met (e.g., hospitalization for signs/symptoms of the disease under study, death due to progression of disease).

10.3.3 Adverse Device Effect (ADE)

10.3.3.1 Definition of ADE

- Any adverse event related to the use of device (includes all hardware components).
 - Includes any event that is a result of a user error or intentional misuse.

10.3.3.2 Definition of Unanticipated adverse device effect (UADE)

- UADE is any serious adverse effect on health or safety, any life-threatening problem or death caused by, or associated with a device, if that effect, problem, or death was not previously identified in nature, severity, or degree of incidence in the application; or any other unanticipated serious problem associated with a device that relates to the rights, safety, or welfare of participants. Note the reporting of UADEs should follow reporting requirements for SAEs/SADEs

10.3.3.3 Definitions of Technical Complaints and Device Deficiencies

- Device Complaint: A quality complaint received in writing, electronically, or orally that alleges deficiencies related to the identity, quality, durability, reliability, safety, effectiveness, or performance of a device product. (In this definition, "effectiveness" refers to the actual function of the device, not to how the participant responds to the action of the device)
- Device Deficiency: Inadequacy of a medical device with respect to its identity, quality, durability, reliability, safety or performance. Device deficiencies include malfunctions, use errors and inadequate labelling.

10.3.3.4 Risks/Precautions

Refer to the SPY Portable Handheld Imager (SPY-PHI) and 1688 Advanced Imaging Modalities (AIM) 4k Platform Manuals for a full description of the risks and precautions

associated with all components of the SPY-PHI and 1688 AIM systems, respectively. The entirety of the Operator Manuals should be read before using the device(s). Failure to follow the instructions and warnings in the manual may result in unsafe operation of the system and/or injury to the subject or operator.

10.3.4 Assessment of Causality

- The investigator is obligated to assess the relationship between study IP, imaging device(s), study procedures and each occurrence of each AE/SAE/ADE.
- A “reasonable possibility” of a relationship conveys that there are facts, evidence, and/or arguments to suggest a causal relationship, rather than a relationship cannot be ruled out.
- The investigator will use clinical judgment to determine the relationship.
- Alternative causes, such as underlying disease(s), concomitant therapy, and other risk factors, as well as the temporal relationship of the event to study IP administration will be considered and investigated.
- The investigator will also consult the IB and/or product information, for marketed products, in his/her assessment.
- For each AE/SAE/ADE, the investigator must document in the medical notes that he/she has reviewed the AE/SAE/ADE and has provided an assessment of causality.
- There may be situations in which an SAE/ADE has occurred and the investigator has minimal information to include in the initial report to the sponsor. However, it is very important that the investigator always make an assessment of causality for every event before the initial transmission of the SAE/ADE data to the sponsor.
- The investigator may change his/her opinion of causality in light of follow-up information and send a SAE/ADE follow-up report with the updated causality assessment.
- The causality assessment between study IP is one of the criteria used when determining regulatory reporting requirements.

Following a review of the relevant data, the causal relationship between the IP and each (S)AE/ADE will be assessed by answering “yes” or “no” to the question “Do you consider that there is a reasonable possibility that the event may have been caused by the IP?”

When making an assessment of causality, the following factors are to be considered when deciding if there is evidence and/or arguments to suggest there is a “reasonable possibility” that an (S)AE/ADE may have been caused by the IP (rather than a relationship cannot be ruled out) or if there is evidence to reasonably deny a causal relationship:

- Has the participant been administered IP?
- Plausibility (i.e., could the event have been caused by the suspect IP? Consider biologic and/or pharmacologic mechanism, half-life, literature evidence, drug class, preclinical and study data, etc.)
- Dechallenge/dose reduction/rechallenge:
 - Dechallenge: Did the (S)AE/ADE resolve or improve after only stopping the dose of the suspect drug without any treatment?

- Dose reduction: Did the (S)AE/ADE resolve or improve after reducing the dose of the suspect drug?
- Rechallenge: Did the (S)AE/ADE reoccur if the suspected drug was reintroduced after having been stopped?
- Laboratory or other test results: a specific lab investigation supports the assessment of the relationship between the (S)AE/ADE and the IP (e.g., based on values pre-, during and post-treatment)
- Available alternative explanations independent of IP exposure; such as other concomitant drugs, device malfunctions, past medical history, concurrent or underlying disease, risk factors including medical and family history, season, location, etc., and strength of the alternative explanation
- Temporal relationship between exposure to the IP and (S)AE/ADE onset and/or resolution. Did the (S)AE/ADE occur in a reasonable temporal relationship to the administration of the IP?
- Finally, judging which are more likely based on all the above contents, factors of reasonable possibility or confounding factors, comprehensive judgment of plausible will be provided.

There may be situations in which an SAE/ADE has occurred and the investigator has minimal information to include in the initial report to the sponsor. While it is very important that the investigator always assesses causality for every event before the initial transmission of the SAE/ADE data to the sponsor, the initial report should be submitted without delay (i.e., within 24 hours of awareness). With limited or insufficient information about the event to make an informed medical judgment and in absence of any indication or evidence to establish a causal relationship, a causality assessment of “no” is to be considered. In such instance, the investigator is expected to obtain additional information regarding the event as soon as possible and to re-evaluate the causality upon receipt of additional information. The medically qualified investigator may revise his/her assessment of causality in light of new information regarding the SAE/ADE and shall send an SAE/ADE follow-up report and update the eCRF with the new information and updated causality assessment.

Device Relatedness

Events will be classified as device related if they meet the following criteria:

- **Not Related:** Any reaction that does not follow a reasonable temporal sequence from administration of the device or surgical procedure, or study intervention AND that is likely to have been produced by the participant’s clinical state or other modes of therapy administered to the participant.
- **Related:** A reaction that follows or may follow a reasonable temporal sequence from administration of the device, surgical procedure, or study intervention AND that follows a known response pattern to the suspected device/surgical procedure/study intervention.

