7.3.1.1 Adverse Device Effects

- ADEs are to be collected via the ADE worksheet and reported to the sponsor within 24 hours of awareness (see [Section 10.3.3.1]).
- Any complaint about a device must be reported regardless of whether the defect or deficiency had any effect on a participant or on study personnel (see [Section 10.3.3.3]).

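### The two device-relatedness classes in Protocol 10.3.4 leave some events in neither class and let events without device involvement count as device related

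*Protocol*

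**What the plan says.** Protocol 10.3.4, under Device Relatedness, opens with "Events will be classified as device related if they meet the following criteria" and then gives two classes.

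- *Related* has two conditions. The first is timing: "A reaction that follows or may follow a reasonable temporal sequence from administration of the device, surgical procedure, or study intervention". The second is joined to it: "AND that follows a known response pattern to the suspected device/surgical procedure/study intervention".
- *Not Related* also has two conditions. The first is "Any reaction that does not follow a reasonable temporal sequence from administration of the device or surgical procedure, or study intervention". The second, again joined by AND, is that the participant's clinical state or other treatment is the likely cause.

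Three other places depend on this classification or bear on it.

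- Protocol 10.3.3.1 defines an adverse device effect (ADE): "Any adverse event related to the use of device (includes all hardware components". User error and intentional misuse are included.
- Protocol 10.3.3.2 makes a serious effect caused by or associated with a device a UADE "if that effect, problem, or death was not previously identified in nature, severity, or degree of incidence in the application". UADEs are reported in the same way as serious events.
- Protocol 7.3.1.1 sets the reporting rule: "ADEs are to be collected via the ADE worksheet and reported to the sponsor within 24 hours of awareness". It attaches no condition of seriousness.

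Protocol 10.3.4 itself starts by obliging the investigator to assess the IP, the imaging device(s) and the study procedures, named as separate items. For the IP it uses a single yes/no question on whether there is a reasonable possibility of causation.

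**The concern.** A relatedness scale should give every event exactly one class, and it should ask about the one cause it is meant to attribute. This one appears to do neither.

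First, requiring a known pattern works against the purpose of a UADE definition, which includes effects that nobody has seen before. Second, because each condition of *Related* can be met through the surgery or the study intervention, an event can be labelled device related when the device played no part.

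Every participant undergoes surgery with a near-infrared imaging device and receives ASP5354, so the question arises for every adverse event after dosing. At stake are whether device effects are attributed correctly, whether a new one is recognised as a UADE, and whether the 24-hour ADE route is used for the right events.

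**Working it through.** The plan gives no figure to reproduce. The check is logical.

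**Step 1: are the classes exhaustive?** Take three yes/no attributes from 10.3.4: T, the timing fits or may fit; K, the event follows a known response pattern; A, another cause is likely. *Related* is T and K. *Not Related* is (not T) and A. There are 2 × 2 × 2 = 8 combinations.

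| T | K | A | Class |
|---|---|---|---|
| yes | yes | yes | Related |
| yes | yes | no | Related |
| yes | no | yes | none |
| yes | no | no | none |
| no | yes | yes | Not Related |
| no | no | yes | Not Related |
| no | yes | no | none |
| no | no | no | none |

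Two combinations are *Related*, two are *Not Related*, and 8 − 2 − 2 = 4 have no class. The fourth row matters most: the timing fits, there is no known pattern and there is no other explanation.

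**Step 2: set the classes beside the UADE definition in 10.3.3.2.** That definition has three alternatives: not previously identified in nature, in severity, or in degree of incidence.

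- *New in nature, timing fits.* There is no known pattern, so the event is not *Related*. The timing is present, so it is not *Not Related* either. It has no class.
- *Known in nature, unexpected severity.* It can follow a known pattern, so it can be *Related*.
- *Known in nature, unexpected incidence.* As for severity, it can be *Related*.

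The conflict is therefore confined to effects of a new nature.

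**Step 3: set the classes beside the ADE definition in 10.3.3.1.**

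- *A complication with a known pattern for lymph node surgery, arising after the operation.* Both conditions are met through the surgical procedure, so it is literally *Related*.
- *Green coloration.* Protocol 7.2.6.1 records it as an AE, and Protocol 2.2.1.2 describes green urine after intravenous ASP5354 in both phase 1 studies. If study intervention includes ASP5354, both conditions are met and it is literally *Related*.

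Either event would then count as an ADE due within 24 hours under 7.3.1.1. Yet 10.3.3.1 ties an ADE to use of the device, and 10.3.4 lists IP, device and procedures separately.

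**Step 4: what other routes catch the event?** Protocol 7.3.1 and 10.3.7 send every SAE to the sponsor within 24 hours, whatever its cause. Non-serious AEs are collected on the eCRF, without a 24-hour rule. Device complaints are reportable under 7.3.1.1, but 10.3.3.3 defines them as alleged deficiencies, so harm from a device working as intended is not clearly covered. The case left without a 24-hour route is a non-serious device effect of a new nature.

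**Step 5: does any planned analysis use the class?** Protocol 9.3.5.1 and SAP 4.7.1 list summaries of TEAEs, IP-related TEAEs and serious TEAEs, among others. Neither specifies an ADE or device-related table.

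**The case against.** The strongest reply is that the surrounding text limits the harm, and much of that stands.

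A reader might infer that an unanticipated device effect can never be classed as related. The documents do not support this: by Step 2, effects unexpected only in severity or incidence can be. A reader might also infer that a serious new device event would go unreported. That does not follow either. A UADE is serious by definition, 10.3.3.2 has its own causal test that does not refer to the *Related* class, and an event meeting the SAE definition reaches the sponsor within 24 hours with a statement of causal relationship to the IP or device (10.3.7). Nor do the documents support a third inference, that reported device-related counts will mix surgical and drug effects, because no such count is planned.

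It is also fair to say that 10.3.4 calls for clinical judgment. An investigator who reads the classes together with 10.3.3.1 would probably not report a wound complication as a device effect, and over-reporting is the safer error. The four unclassified combinations are not equally important: two have no plausible timing and should be easy to place in practice.

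What remains is that judgment has to override the written criteria in both directions. The SAE route does not help with non-serious effects. An SAE without a usable device classification also weakens the later steps: the sponsor's evaluation of ADEs for expedited reporting (10.3.7) and any notice to the device manufacturer (7.3.4).

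**Conclusion.** The rule is wrong as written, with limited consequences. The two classes are not exhaustive: 4 of 8 logical combinations have no class, including a well-timed device effect of a new nature with no other explanation. They also admit events that have nothing to do with the device. This conflicts with 10.3.3.1, with the new-in-nature part of 10.3.3.2, and with the separate assessments that 10.3.4 itself requires.

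At risk are device attribution, UADE classification, and 24-hour ADE reporting of non-serious new device effects. The dose decision, the efficacy endpoints and the planned safety tables are unaffected. The documents allow no estimate of how many events would be involved.

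The conclusion rests on a literal reading of the criteria. The green-coloration example further assumes that study intervention includes ASP5354. The eCRF and the ADE worksheet are not among the documents, so they may already separate device from procedure.

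**What to change.** Replace the two definitions in Protocol 10.3.4 with one question parallel to the IP question: is there a reasonable possibility that the event was caused by the imaging device, including user error? Yes is *Related*; no is *Not Related*. Every event then has exactly one class.

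Keep a known response pattern as supporting evidence, not as a required condition. Remove surgical procedure and study intervention from the device criteria. Record relationship to study procedures as its own item if the eCRF or ADE worksheet does not already do so.

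The cost is a change of protocol wording and perhaps one form item; design and sample size do not change. The downside is that investigators rely on judgment in place of a pattern test, as they already do for the IP.
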